5.1.3 Post-treatment evaluation

Data to be obtained at completion of study:

- Physical examination
- Toxicity assessment
- Vital signs
- Weight
- Serum chemistries
- CBC with differential
- Radiologic assessment of tumor burden by CT scan. All sites of tumor progression or metastases will be noted
- Progression-free and overall survival will be determined

Patients who have an ongoing Grade 4 or serious adverse event at the time of discontinuation from study drug treatment will continue to be followed at monthly intervals, until resolution of toxicity to < Grade 2.

5.1.3.1 Table of required data

Table 5.1. Evaluation and visit schedule

Examination	Screening		Every Cycle	Cycles 1- 6	Every 2 cycles	End
	-28 days	-14 days	Day 1	Day 15		
Screening ^a		X				
History		X	X*	X		X
Physical Exam		X	X*	X		X
Vital Signs		X	X*	X		X
Height		X				
Weight		X	X*	X		X
ECOG PS		X	X*			X
Pregnancy Test ^b		X				
Hematology ^c		X	X*	X		X
Serum Chemistry ^d		X	X*			X
Serum Lipid Profile ^e		X			X	X
Radiologic Assessment of Tumor Burden ^f	X				X	X
Secretory proteins, serum chromogranin ^g	X				X	X
Prior/concomitant medication		X	continuous -----			
Adverse events		X	continuous -----			

* Screening tests do not need to be repeated for cycle 1.

^a Screening includes review of: demography/informed consent, inclusion/exclusion criteria, relevant medical history/concomitant medications, diagnosis and extent of cancer

^b For women of child-bearing potential: Women of childbearing potential must have a negative serum pregnancy test within 14 days of enrollment. Acceptable contraception should be used while on study and for at least 30 days after the last dose of RAD001.

^c Hematology must include: hemoglobin, hematocrit, platelets, total white blood cell count (WBC) and differential

^d Serum chemistry should be performed while fasting and include: fasting glucose, sodium, potassium, chloride, bicarbonate, creatinine, blood urea nitrogen, albumin, total protein, SGOT (AST), SGPT (ALT), total bilirubin, alkaline phosphatase, calcium, magnesium, phosphate.

^e Fasting serum lipid profile (repeated every three months) must include: total cholesterol, triglycerides, LDL, and HDL

^f Screening radiologic tests include abdominal and pelvic CT or MRI and must be done within 28 days of first RAD001 and temozolomide dose. Radiological scans documenting target lesions should be repeated every two months. If an initial observation of a partial or complete response is made, a confirmation scan should be done no sooner than 4 weeks and no more than 6 weeks after the initial observation. The same type of scan should be used at each evaluation.

^g Assessment of secretory proteins will be performed within 28 days prior to initiation of therapy.

6 Efficacy assessments

The primary efficacy endpoint is objective response rate as determined by radiology review. Important secondary endpoints are response duration and progression-free survival.

6.1 Criteria for response

The Response Evaluation Criteria in Solid Tumors (RECIST) guidelines will be employed in this study. For the purposes of this study, target lesions are defined as metastatic lesions that are bidirectionally measurable with one diameter measuring at least 2 cm (or 1 cm with spiral CT scan). All lesions up to a maximum of 10 lesions representative of all involved organs should be identified as target lesions and will be recorded and measured at baseline. Target lesions should be selected on the basis of their size (lesions with the longest diameter) and their suitability for accurate repetitive measurements (either by imaging techniques or

clinically). A sum of the longest diameter (LD) for all target lesions will be calculated and reported as the baseline sum LD. The baseline sum LD will be used as reference to further characterize the objective tumor response of the measurable dimension of the disease.

Measurable disease: lesions that can be accurately measured in at least one dimension (longest diameter to be recorded) as ≥ 20 mm with conventional techniques or as ≥ 10 mm with spiral CT scan.

Non-measurable disease: all other lesions, including small lesions (longest diameter < 20 mm with conventional techniques or < 10 mm with spiral CT scan).

Complete response (CR): complete disappearance of all target lesions, confirmed by repeat assessments at no less than 4 weeks after the criteria for response are first met.

Partial response (PR): at least a 30% decrease in the sum of the longest diameter of target lesions, taking as reference the baseline sum longest diameter. This must be confirmed by repeat assessment at no less than 4 weeks after the criteria for response are first met.

Progressive disease (PD): at least a 20% increase in the sum of the longest diameter of target lesions, taking as reference the smallest sum longest diameter recorded since the treatment started or the appearance of one or more new lesions.

Stable Disease (SD): neither sufficient decrease to qualify for partial response nor sufficient increase to qualify for progressive disease, taking as reference the smallest sum longest diameter since the treatment started.

Non-target Lesions: all other lesions (or sites of disease) not included in the “target disease” definition should be identified as non-target lesions and should also be recorded at baseline. Measurements are not required and these lesions should be followed as “present” or “absent”.

Complete Response: Disappearance of all non-target lesions.

Non-complete response/Non-progression: Persistence of one or more non-target lesions.

Progression: Appearance of one or more new lesions. Unequivocal progression of existing non-target lesions.

Cytology and Histology: if the measurable disease is restricted to a solitary lesion, its neoplastic nature should ideally be confirmed by cytology or histology. These techniques can be used to differentiate between PR and CR in rare cases.

The cytological confirmation of the neoplastic origin of any effusion that appears or worsens during treatment when the measurable tumor has met criteria for response or stable disease is mandatory to differentiate between response, stable disease, and progressive disease

Evaluation of Best Overall Response: the best overall response recorded from the start of the treatment until disease progression/recurrence (taking as reference for progressive disease the smallest measurements recorded since the treatment started). In general, the patient's best response assignment will depend on the achievement of both measurement and confirmation criteria.

Target Lesions	Non-target Lesions	New Lesions	Overall Response
CR	CR	No	CR
CR	Non-CR/Non-PD	No	PR
PR	Non-PD	No	PR
SD	Non-PD	No	SD
PD	Any	Yes or No	PD
Any	PD	Yes or No	PD
Any	Any	Yes	PD

Note:

Patients with a global deterioration of health status requiring discontinuation of treatment without objective evidence of disease progression at that time should be reported as “symptomatic deterioration”. Every effort should be made to document the objective progression even after discontinuation of treatment.

In some circumstances it may be difficult to distinguish residual disease from normal tissue. When the evaluation of complete response depends upon this determination, it is recommended that the residual lesion be investigated (fine needle aspirate/biopsy) before confirming the complete response status.

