4.5.3 Prohibited medications

1. Growth factors cannot be used to induce elevations in neutrophil count for the purposes of administration of Temozolomide on the scheduled dosing interval or to allow treatment with Temozolomide at a higher dose.
2. Use of erythropoietin is allowed.
3. No other investigational drugs will be allowed during the study.
4. Patients must be instructed not to take any additional medications (including over-the-counter products) during the trial without prior consultation with the investigator. All medications taken within 30 days of screening should be recorded. If concomitant therapy must be added or changed, the reason and name of the drug/therapy should be recorded.
5. In general, the use of any concomitant medication/therapies deemed necessary for the care of the patient are allowed, including drugs given prophylactically (e.g. antiemetics +/- steroids), with the following exceptions:
 - no other investigational therapy should be given to patients
 - no chronic treatment with systemic steroids or another immunosuppressive agent
 - no anticancer agents other than the study medications administered as part of this study protocol should be given to patients. If such agents are required for a patient then the patient must first be withdrawn from the study.
 - leukocyte growth factors (e.g. G-CSF and GM-CSF) are not to be administered systematically but may be prescribed by the investigator for severe neutropenia if this is thought to be appropriate.
 - no live vaccines should be administered to patient due to immunosuppressant potential of RAD001.
 - drugs or substances known to be inhibitors or inducers of the isoenzyme CYP3A (Table 4.7) cannot be administered in association with RAD001 as these can alter

metabolism. Strong inhibitors or inducers of the isoenzyme CYP3A cannot be administered as systemic therapy.

Table. 4.7 Clinically relevant drug interaction: substrates, inducers and inhibitors of isoenzyme CYP3A

Substrates		
Antibiotics: clarithromycin erythromycin NOT azithromycin telithromycin	Calcium Channel Blockers: amlodipine diltiazem felodipine nifedipine nisoldipine nitrendipine verapamil	
Anti-arrhythmics: quinidine	HMG CoA Reductase Inhibitors: atorvastatin cerivastatin lovastatin NOT pravastatin simvastatin	

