6.3 Confirmation Measurement/Duration of Response

Confirmation: To be assigned a status of PR or CR, changes in tumor measurements must be confirmed by repeat studies that should be performed no less than 4 weeks after the criteria for response are first met. In the case of SD, follow-up measurements must have met the SD criteria at least once after study entry at a minimum interval of 6 weeks.

Duration of Overall Response: The duration of overall response is measured from the time measurement criteria are met for CR/PR (whichever is first recorded) until the first date that recurrent or progressive disease is objectively documented (taking as reference for progressive disease the smallest measurements recorded since the treatment started).

The duration of overall complete response is measured from the time measurement criteria are first met for CR until the first date that recurrent disease is objectively documented.

Duration of Stable Disease: Stable disease is measured from the start of the treatment until the criteria for progression are met, taking as reference the smallest measurements recorded since the treatment started.

Progression Free Survival (PFS): PFS is defined as the time from the date of first study treatment to the date of the first documented disease progression or death due to any cause. If a patient has not progressed or died at the date of the analysis cut-off or when he/she receives any further anti-cancer therapy, PFS is censored at the time of the last tumor assessment before the cut-off or the anti-cancer therapy date.

7 Safety assessments

Safety assessments will consist of monitoring and recording all adverse events and serious adverse events, the regular monitoring of hematology, blood chemistry and urine values, regular measurement of vital signs and the performance of physical examinations.

These assessments should be performed within ± 2 days of the scheduled day of assessment except for adverse events that will be evaluated continuously through the study. Safety and tolerability will be assessed according to the NIH/NCI CTCAE <http://ctep.cancer.gov/forms/CTCAEv3.pdf>.

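### Best overall response, the primary endpoint, has no stop at further anti-cancer therapy although PFS does, so shrinkage after on-study local therapy could be scored as response to the study drugs

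*Combined protocol and SAP*

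**What the plan says.** The opening of Section 6 names the endpoint: "The primary efficacy endpoint is objective response rate as determined by radiology review". Section 6.1 (Evaluation of Best Overall Response) sets its window: "the best overall response recorded from the start of the treatment until disease progression/recurrence". Progression or recurrence is the only stop.

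Section 6.3 treats PFS differently. For a patient who has not progressed or died, "PFS is censored at the time of the last tumor assessment before the cut-off or the anti-cancer therapy date". Response duration, also in 6.3, again has no such stop and runs "until the first date that recurrent or progressive disease is objectively documented".

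Section 4.5.3, item 5, starts from a general permission, "the use of any concomitant medication/therapies deemed necessary for the care of the patient are allowed", and then lists exceptions. The relevant one reads "no anticancer agents other than the study medications administered as part of this study protocol should be given to patients", with withdrawal required before such agents are given. Radiation, embolization, ablation and resection are not on the list.

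Section 10.1 counts responses without giving a window: stop at 0 of 17, and recommend further study at 3 or more of 32. Section 10.2 adds only an estimate of the response rate with a 95% confidence interval.

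**The concern.** The authors foresaw that a patient might receive other anti-cancer treatment before progressing, and they protected a secondary endpoint against it. The primary endpoint has no such protection.

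Take a patient with stable disease on RAD001 who has a target lesion irradiated, ablated, embolized without drug, or resected. If the sum of longest diameters then falls at least 30% below baseline and a repeat scan confirms it, 6.1 as written makes the patient a PR or CR. The PFS rule would already have censored that patient. Confirmation after four weeks or more does not screen this out, since a lesion removed or shrunk by local therapy stays that way on the repeat scan.

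The error runs in one direction: it can add a response but cannot remove one. The decision rule is also sensitive to single patients. One response among 17 prevents the early stop, and three among 32 give a positive conclusion.

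**Working it through.** **Inputs (Section 10.1).** Stage sizes 17 and 15; stop if 0 of 17; go if the total is at least 3 of 32; uninteresting rate 5%, target rate 20%.

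**Formulas.** With true rate p:
- Early stop = (1 − p)^17.
- Go(p) = Σ over x = 1 to 17 of Bin(x; 17, p) × P[Bin(15, p) ≥ 3 − x].

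**Step 1: reproduce the plan's figures.**
- Early stop: 0.95^17 = 0.418 and 0.80^17 = 0.023 (stated 0.42 and 0.02).
- Go(0.20) = 0.955 (stated power 0.95).
- Go(0.05), by number of stage 1 responses: 0.3741 × 0.1710 (one) + 0.1575 × 0.5367 (two) + 0.0503 (three or more) = 0.0640 + 0.0845 + 0.0503 = 0.199.
- The stated type I error is 0.18. The written rule at 32 gives 0.199; with 17 + 13 = 30 eligible patients it gives 0.178, which may be the source of the stated figure (30/0.95 = 31.6, rounded up to 32). The baseline below is 0.199, the written rule at 32.

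**Step 2: add misattributed responses.** Let q be the share of true non-responders scored as responders only because of local therapy. The documents give no value, so q is an assumption. The effective rate is p_eff = 0.05 + 0.95q.

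| q (assumed) | p_eff | Early stop | Go probability |
|---|---|---|---|
| 0 | 0.0500 | 0.418 | 0.199 |
| 0.5% | 0.0548 | 0.384 | 0.237 |
| 1% | 0.0595 | 0.352 | 0.277 |
| 2% | 0.0690 | 0.297 | 0.358 |
| 1/32 | 0.0797 | 0.244 | 0.447 |

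**Step 3: allow for timing.** The table assumes that stage 1 false responses are already counted at the 17-patient review. Suppose instead that they appear only afterwards: the review sees the true 5% rate, each remaining stage 1 non-responder then converts with probability q, and stage 2 patients respond at p_eff. Early stopping stays at 0.418, and the go probability at q = 1/32 is 0.371 instead of 0.447.

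**Step 4: check when scans take place.** Section 5.1.2.3 places CT after every two cycles, under evaluations during treatment. Section 5.1.3 and the End column of Table 5.1 add one CT at completion. Section 4.1 lets RAD001 continue until progression or toxicity. A locally treated patient who stays on RAD001 would therefore be rescanned and could be confirmed. One who has stopped would normally have a single further scan, which cannot by itself confirm a response.

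**The case against.** The strongest reply is that the sequence is unlikely. Section 4.5.3 reads as supportive-care language: its example is antiemetics with or without steroids, and Section 4.5.2 illustrates non-drug therapies with physical therapy and transfusions. On that reading, omitting radiation or surgery is a drafting gap and not permission to treat a target lesion and stay on study. Drug-based chemoembolization may already be caught as an agent. There are partial checks too: radiology review, the coordinating center's duty to verify response (Appendix B, Section 2.2), and the recording of significant non-drug therapies. Section 6.1 also allows up to ten target lesions, so treating one of several need not lower the sum by 30%.

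This stands as a limit on frequency. It does not supply the missing rule. None of these checks tells the radiologist or the analyst to disregard scans after local therapy, and even where withdrawal applies, nothing says that later scans are excluded.

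Three stronger readings are tempting, and the documents do not support them.
- **A large exposed group after toxicity stops.** Adding the discontinuations in Section 1.2 (6 neuropathy, 4 thrombocytopenia, 1 rash, 1 neutropenia, 4 infection) gives 16 of 29. Those categories are not stated to be mutually exclusive, the regimen contained thalidomide, and the count is of toxicity stops, not of patients who went on to local therapy. With one End CT scheduled, the off-treatment route is narrow. It is not fully shut, because footnote f of Table 5.1 gives no end to two-monthly scans and asks for a confirmation scan after an initial response.
- **Local therapy is expected on study.** Inclusion criterion 2 mentions radiation, chemoembolization and cryotherapy, but only as treatment before entry.
- **A known, large inflation of the false-go probability.** Every figure above 0.199 depends on an assumed q.

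**Conclusion.** The mismatch is real. The primary endpoint's window lacks the stop that PFS has, and Section 4.5.3 does not close the gap for non-drug local therapy. The realistic route is local treatment of a target lesion in a non-progressing patient who is still being scanned.

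At a true 5% response rate, the go probability moves from 0.20 to 0.24–0.28 if 0.5% to 1% of non-responders are misattributed, to 0.36 at 2%, and to 0.45 at 1 in 32 (0.37 if stage 1 patients' false responses come after the review). These are sensitivity figures and not estimates, since the documents do not say how often such therapy would occur; if it never occurs, nothing changes. The point is a cheap improvement to the endpoint definition. It does not show that the response rate is or will be inflated.

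**What to change.** In Section 6.1, end the best-response window at *disease progression/recurrence or the start of any further anti-cancer therapy (systemic, radiation, embolization, ablation or resection of tumor), whichever is first*. In Section 10.1, state that responses first met after that date do not count toward the stage 1 or final totals.

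This is an analysis rule only and does not change which treatments are permitted. It costs two sentences and uses a date that PFS censoring already needs; visits, scans and sample size are unaffected. The downside is that the reported response rate may be slightly lower.

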6.2 Guidelines for Evaluation of Measurable Disease

Clinical Lesions. Clinical lesions will only be considered measurable when they are superficial (e.g. skin nodules, palpable lymph nodes). For the case of skin lesions, documentation by color photography including a ruler to estimate the size of the lesion is recommended.

Chest X-ray. Lesions on chest X-ray are acceptable as measurable lesions when they are clearly defined and surrounded by aerated lung. However, CT scan is preferable.

CT scan. Conventional CT scan should be performed with cuts of 10mm or less in slice thickness contiguously. Spiral CT scan should be performed using a 5mm contiguous reconstruction algorithm. This applies to the chest, abdomen, and pelvis. Head & neck and extremities usually require specific protocols.

Ultrasound. Ultrasound should not be used to measure tumor lesions that are clinically not easily accessible when the primary endpoint of the study is objective response evaluation. It is a possible alternative to clinical measurements of superficial palpable nodes, subcutaneous lesions, and thyroid nodules. Ultrasound may also be useful to confirm the complete disappearance of superficial lesions usually assessed by clinical examination.

6.3 Confirmation Measurement/Duration of Response

Confirmation: To be assigned a status of PR or CR, changes in tumor measurements must be confirmed by repeat studies that should be performed no less than 4 weeks after the criteria for response are first met. In the case of SD, follow-up measurements must have met the SD criteria at least once after study entry at a minimum interval of 6 weeks.

Duration of Overall Response: The duration of overall response is measured from the time measurement criteria are met for CR/PR (whichever is first recorded) until the first date that recurrent or progressive disease is objectively documented (taking as reference for progressive disease the smallest measurements recorded since the treatment started).

The duration of overall complete response is measured from the time measurement criteria are first met for CR until the first date that recurrent disease is objectively documented.

Duration of Stable Disease: Stable disease is measured from the start of the treatment until the criteria for progression are met, taking as reference the smallest measurements recorded since the treatment started.

Progression Free Survival (PFS): PFS is defined as the time from the date of first study treatment to the date of the first documented disease progression or death due to any cause. If a patient has not progressed or died at the date of the analysis cut-off or when he/she receives any further anti-cancer therapy, PFS is censored at the time of the last tumor assessment before the cut-off or the anti-cancer therapy date.

7 Safety assessments

Safety assessments will consist of monitoring and recording all adverse events and serious adverse events, the regular monitoring of hematology, blood chemistry and urine values, regular measurement of vital signs and the performance of physical examinations.

These assessments should be performed within ± 2 days of the scheduled day of assessment except for adverse events that will be evaluated continuously through the study. Safety and tolerability will be assessed according to the NIH/NCI CTCAE <http://ctep.cancer.gov/forms/CTCAEv3.pdf>.

7.1 Adverse events

Information about all adverse events, whether volunteered by the subject, discovered by investigator questioning, or detected through physical examination, laboratory test or other means, will be collected and recorded and followed as appropriate.

An adverse event is the appearance or worsening of any undesirable sign, symptom, or medical condition occurring after starting the study drug even if the event is not considered to be related to study drug. Medical conditions/diseases present before starting study drug are only considered adverse events if they worsen after starting study drug. Abnormal laboratory values or test results constitute adverse events only if they induce clinical signs or symptoms, are considered clinically significant, or require therapy.

The occurrence of adverse events should be sought by non-directive questioning of the patient at each visit during the study. Adverse events also may be detected when they are volunteered by the patient during or between visits or through physical examination, laboratory test, or other assessments. As far as possible, each adverse event should be evaluated to determine:

1. the severity grade (mild, moderate, severe) or (grade 1-4)
2. its relationship to the study drug(s) (suspected/not suspected)
3. its duration (start and end dates or if continuing at final exam)
4. action taken (no action taken; study drug dosage adjusted/temporarily interrupted; study drug permanently discontinued due to this adverse event; concomitant medication taken; non-drug therapy given; hospitalization/prolonged hospitalization)
5. whether it constitutes a serious adverse event (SAE)

All adverse events should be treated appropriately. Such treatment may include changes in study drug treatment including possible interruption or discontinuation, starting or stopping concomitant treatments, changes in the frequency or nature of assessments, hospitalization, or any other medically required intervention. Once an adverse event is detected, it should be followed until its resolution, and assessment should be made at each visit (or more frequently, if necessary) of any changes in severity, the suspected relationship to the study drug, the interventions required to treat it, and the outcome.

Information about common side effects already known about the investigational drug can be found in the [\[Investigators' Brochure\]](#) or will be communicated between IB updates in the form of Investigator Notifications. This information will be included in the patient informed consent and should be discussed with the patient during the study as needed.

